11. MEASUREMENT OF EFFECT

Although response is not the primary endpoint of this trial, participants with measurable disease will be assessed by standard criteria. For the purposes of this study, participants should be re-evaluated every 8 weeks.

11.1 Antitumor Effect – Solid Tumors

For the purposes of this study, participants should be re-evaluated for response every 8 weeks (\pm 1 week).

Response and progression will be evaluated in this study using the new international criteria proposed by the Response Evaluation Criteria in Solid Tumors (RECIST) guideline (version 1.1) [*Eur J Ca* 45:228-247, 2009]. Changes in the largest diameter (unidimensional measurement) of the tumor lesions and the shortest diameter in the case of malignant lymph nodes are used in the RECIST criteria.

11.1.1 Definitions

- **Evaluable for Target Disease response.** Only those participants who have measurable disease present at baseline, have received at least one cycle of therapy, and have had their disease re-evaluated will be considered evaluable for target disease response. These participants will have their response classified according to the definitions stated below. (Note: Participants who exhibit objective disease progression prior to the end of cycle 1 will also be considered evaluable.)
- **Evaluable Non-Target Disease Response.** Participants who have lesions present at baseline that are evaluable but do not meet the definitions of measurable disease, have received at least one cycle of therapy, and have had their disease re-evaluated will be considered evaluable for non-target disease. The response assessment is based on the presence, absence, or unequivocal progression of the lesions.

11.1.2 Disease Parameters

- Measurable disease. Measurable lesions are defined as those that can be accurately measured in at least one dimension (longest diameter to be recorded) as ≥ 20 mm by chest x-ray or ≥ 10 mm with CT scan, MRI, or calipers by clinical exam. All tumor measurements must be recorded in millimeters (or decimal fractions of centimeters).
- Malignant lymph nodes. To be considered pathologically enlarged and measurable, a lymph node must be ≥ 15 mm in short axis when assessed by CT scan (CT scan slice thickness recommended to be no greater than 5 mm). At baseline and in follow-up, only the short axis will be measured and followed.
- Non-measurable disease. All other lesions (or sites of disease), including small lesions (longest diameter <10 mm or pathological lymph nodes with ≥ 10 to <15 mm short axis), are considered non-measurable disease. Bone lesions, leptomeningeal disease, ascites, pleural/pericardial effusions, lymphangitis cutis/pulmonitis, inflammatory breast disease, abdominal masses (not followed by CT or MRI), and cystic lesions are all considered non-measurable.

Note: Cystic lesions that meet the criteria for radiographically defined simple cysts should not be considered as malignant lesions (neither measurable nor non-measurable) since they are, by definition, simple cysts.

‘Cystic lesions’ thought to represent cystic metastases can be considered as measurable lesions, if they meet the definition of measurability described above. However, if non-cystic lesions are present in the same participant, these are preferred for selection as target lesions.

- Target lesions. All measurable lesions up to a maximum of 2 lesions per organ and 5 lesions in total, representative of all involved organs, should be identified as **target lesions** and recorded and measured at baseline. Target lesions should be selected on the basis of their size (lesions with the longest diameter), be representative of all involved organs, but in addition should be those that lend themselves to reproducible repeated measurements. It may be the case that, on occasion, the largest lesion does not lend itself to reproducible measurement in which circumstance the next largest lesion which can be measured reproducibly should be selected. A sum of the diameters (longest for non-nodal lesions, short axis for nodal lesions) for all target lesions will be calculated and reported as the baseline sum diameters. If lymph nodes are to be included in the sum, then only the short axis is added into the sum. The baseline sum diameters will be used as reference to further characterize any objective tumor regression in the measurable dimension of the disease.
- Non-target lesions. All other lesions (or sites of disease) including any

measurable lesions over and above the 5 target lesions should be identified as **non-target lesions** and should also be recorded at baseline. Measurements of these lesions are not required, but the presence, absence, or in rare cases unequivocal progression of each should be noted throughout follow up.

11.1.3 Methods for Evaluation of Disease

All measurements should be taken and recorded in metric notation using a ruler, calipers, or a digital measurement tool. All baseline evaluations should be performed as closely as possible to the beginning of treatment and never more than 4 weeks before the beginning of the treatment.

The same method of assessment and the same technique should be used to characterize each identified and reported lesion at baseline and during follow-up. Imaging-based evaluation is preferred to evaluation by clinical examination unless the lesion(s) being followed cannot be imaged but are assessable by clinical exam.

- Clinical lesions. Clinical lesions will only be considered measurable when they are superficial (*e.g.*, skin nodules and palpable lymph nodes) and ≥ 10 mm in diameter as assessed using calipers (*e.g.*, skin nodules). In the case of skin lesions, documentation by color photography, including a ruler to estimate the size of the lesion, is recommended.
- Chest x-ray. Lesions on chest x-ray are acceptable as measurable lesions when they are clearly defined and surrounded by aerated lung; however, CT is preferable.
- Conventional CT and MRI. This guideline has defined measurability of lesions on CT scan based on the assumption that CT thickness is 5mm or less. If CT scans have slice thickness greater than 5 mm, the minimum size of a measurable lesion should be twice the slice thickness. MRI is also acceptable in certain situations (*e.g.* for body scans).
- Use of MRI remains a complex issue. MRI has excellent contrast, spatial, and temporal resolution; however, there are many image acquisition variables involved in MRI, which greatly impact image quality, lesion conspicuity, and measurement. Furthermore, the availability of MRI is variable globally. As with CT, if an MRI is performed, the technical specifications of the scanning sequences used should be optimized for the evaluation of the type and site of disease. Furthermore, as with CT, the modality used at follow-up should be the same as was used at baseline and the lesions should be measured/assessed on the same pulse sequence. It is beyond the scope of the RECIST guidelines to prescribe specific MRI pulse sequence parameters for all scanners, body parts, and diseases. Ideally, the same type of scanner should be used and the image acquisition protocol should be followed as closely as possible to prior scans.

Body scans should be performed with breath-hold scanning techniques, if possible.

- **FDG-PET**. While FDG-PET response assessments need additional study, it is sometimes reasonable to incorporate the use of FDG-PET scanning to complement CT scanning in assessment of progression (particularly possible 'new' disease). New lesions on the basis of FDG-PET imaging can be identified according to the following algorithm:
 - Negative FDG-PET at baseline, with a positive FDG-PET at follow-up is a sign of PD based on a new lesion.
 - No FDG-PET at baseline and a positive FDG-PET at follow-up: If the positive FDG-PET at follow-up corresponds to a new site of disease confirmed by CT, this is PD. If the positive FDG-PET at follow-up is not confirmed as a new site of disease on CT, additional follow-up CT scans are needed to determine if there is truly progression occurring at that site (if so, the date of PD will be the date of the initial abnormal FDG-PET scan). If the positive FDG-PET at follow-up corresponds to a pre-existing site of disease on CT that is not progressing on the basis of the anatomic images, this is not PD.
 - FDG-PET may be used to upgrade a response to a CR in a manner similar to a biopsy in cases where a residual radiographic abnormality is thought to represent fibrosis or scarring. The use of FDG-PET in this circumstance should be prospectively described in the protocol and supported by disease-specific medical literature for the indication. However, it must be acknowledged that both approaches may lead to false positive CR due to limitations of FDG-PET and biopsy resolution/sensitivity.

Note: A 'positive' FDG-PET scan lesion means one which is FDG avid with an uptake greater than twice that of the surrounding tissue on the attenuation corrected image.

- **PET-CT**. At present, the low dose or attenuation correction CT portion of a combined PET-CT is not always of optimal diagnostic CT quality for use with RECIST measurements. However, if the site can document that the CT performed as part of a PET-CT is of identical diagnostic quality to a diagnostic CT (with IV and oral contrast), then the CT portion of the PET-CT can be used for RECIST measurements and can be used interchangeably with conventional CT in accurately measuring cancer lesions over time. Note, however, that the PET portion of the CT introduces additional data which may bias an investigator if it is not routinely or serially performed.
- **Tumor markers**. Tumor markers alone cannot be used to assess response. If markers are initially above the upper normal limit, they must normalize for a participant to be considered in complete clinical response. Specific guidelines for both CA-125 response (in recurrent ovarian cancer) and PSA response (in recurrent prostate cancer) have been published [*JNCI* 96:487-488, 2004; *J Clin*

Oncol 17, 3461-3467, 1999; *J Clin Oncol* 26:1148-1159, 2008]. In addition, the Gynecologic Cancer Intergroup has developed CA-125 progression criteria which are to be integrated with objective tumor assessment for use in first-line trials in ovarian cancer [JNCI 92:1534-1535, 2000].

- Cytology, Histology. These techniques can be used to differentiate between partial responses (PR) and complete responses (CR) in rare cases (e.g., residual lesions in tumor types, such as germ cell tumors, where known residual benign tumors can remain).
- The cytological confirmation of the neoplastic origin of any effusion that appears or worsens during treatment when the measurable tumor has met criteria for response or stable disease is mandatory to differentiate between response or stable disease (an effusion may be a side effect of the treatment) and progressive disease.

11.1.3.1 Evaluation of Target Lesions

- Complete Response (CR): Disappearance of all target lesions. Any pathological lymph nodes (whether target or non-target) must have reduction in short axis to <10 mm.
- Partial Response (PR): At least a 30% decrease in the sum of the diameters of target lesions, taking as reference the baseline sum diameters.
- Progressive Disease (PD): At least a 20% increase in the sum of the diameters of target lesions, taking as reference the smallest sum on study (this includes the baseline sum if that is the smallest on study). In addition to the relative increase of 20%, the sum must also demonstrate an absolute increase of at least 5 mm. (Note: the appearance of one or more new lesions is also considered progressions).

Immunotherapeutic agents such as pembrolizumab may produce antitumor effects by potentiating endogenous cancer-specific immune responses. The response patterns seen with such an approach may extend beyond the typical time course of responses seen with cytotoxic agents and can manifest a clinical response after an initial increase in tumor burden or even the appearance of new lesions.

Patients with initial PD will be allowed to stay on trial with a repeat scan in 4 weeks. If repeat imaging confirms PD, patients will be discontinued from study therapy.

- Stable Disease (SD): Neither sufficient shrinkage to qualify for PR nor sufficient increase to qualify for PD, taking as reference the smallest sum diameters while on study.

11.1.3.2 Evaluation of Non-Target Lesions

- **Complete Response (CR):** Disappearance of all non-target lesions and normalization of tumor marker level. All lymph nodes must be non-pathological in size (<10 mm short axis).
- Note: If tumor markers are initially above the upper normal limit, they must normalize for a patient to be considered in complete clinical response.
- **Non-CR/Non-PD:** Persistence of one or more non-target lesion(s) and/or maintenance of tumor marker level above the normal limits.
- **Progressive Disease (PD):** Appearance of one or more new lesions and/or *unequivocal progression* of existing non-target lesions. *Unequivocal progression* should not normally trump target lesion status. It must be representative of overall disease status change, not a single lesion increase.

Although a clear progression of “non-target” lesions only is exceptional, the opinion of the treating physician should prevail in such circumstances, and the progression status should be confirmed at a later time by the review panel (or Principal Investigator).

11.1.3.3 Evaluation of New Lesions

The finding of a new lesion should be unequivocal (i.e. not due to difference in scanning technique, imaging modality, or findings thought to represent something other than tumor (for example, some ‘new’ bone lesions may be simply healing or flare of pre-existing lesions). However, a lesion identified on a follow-up scan in an anatomical location that was not scanned at baseline is considered new and will indicate PD. If a new lesion is equivocal (because of small size etc.), follow-up evaluation will clarify if it truly represents new disease and if PD is confirmed, progression should be declared using the date of the initial scan on which the lesion was discovered.

11.1.3.4 Evaluation of Best Overall Response

The best overall response is the best response recorded from the start of the treatment until disease progression/recurrence (taking as reference for progressive disease the smallest measurements recorded since the treatment started). The patient's best response assignment will depend on the achievement of both measurement and confirmation criteria.

For Participants with Measurable Disease (i.e., Target Disease)

Target Lesions	Non-Target Lesions	New Lesions	Overall Response	Best Overall Response when Confirmation is Required*
----------------	--------------------	-------------	------------------	--

CR	CR	No	CR	≥ 4 wks Confirmation**	
CR	Non-CR/Non-PD	No	PR	≥ 4 wks Confirmation**	
CR	Not evaluated	No	PR		
PR	Non-CR/Non-PD/not evaluated	No	PR		
SD	Non-CR/Non-PD/not evaluated	No	SD	Documented at least once ≥ 4 wks from baseline**	
PD	Any	Yes or No	PD	no prior SD, PR or CR	
Any	PD***	Yes or No	PD		
Any	Any	Yes	PD		

* See RECIST 1.1 manuscript for further details on what is evidence of a new lesion.
 
** Only for non-randomized trials with response as primary endpoint.
 
*** In exceptional circumstances, unequivocal progression in non-target lesions may be accepted as disease progression.
					

Note: Participants with a global deterioration of health status requiring discontinuation of treatment without objective evidence of disease progression at that time should be reported as “symptomatic deterioration.” Every effort should be made to document the objective progression even after discontinuation of treatment.
					

For Participants with Non-Measurable Disease (*i.e.*, Non-Target Disease)

Non-Target Lesions	New Lesions	Overall Response
CR	No	CR
Non-CR/non-PD	No	Non-CR/non-PD*
Not all evaluated	No	not evaluated
Unequivocal PD	Yes or No	PD
Any	Yes	PD

* ‘Non-CR/non-PD’ is preferred over ‘stable disease’ for non-target disease since SD is increasingly used as an endpoint for assessment of efficacy in some trials so to assign this category when no lesions can be measured is not advised

11.1.4 Duration of Response

- **Duration of overall response:** The duration of overall response is measured from the time measurement criteria are met for CR or PR (whichever is first recorded) until the first date that recurrent or progressive disease is objectively documented (taking as reference for progressive disease the smallest measurements recorded since the treatment started, or death due to any cause. Participants without events reported are censored at the last disease evaluation).

- Duration of overall complete response: The duration of overall CR is measured from the time measurement criteria are first met for CR until the first date that progressive disease is objectively documented, or death due to any cause. Participants without events reported are censored at the last disease evaluation.
- Duration of stable disease: Stable disease is measured from the start of the treatment until the criteria for progression are met, taking as reference the smallest measurements recorded since the treatment started, including the baseline measurements.

11.1.5 Progression-Free Survival, Overall Survival and Time to Progression:

- Overall Survival: Overall Survival (OS) is defined as the time from randomization (or registration) to death due to any cause, or censored at date last known alive.
- Progression-Free Survival: Progression-Free Survival (PFS) is defined as the time from randomization (or registration) to the earlier of progression or death due to any cause. Participants alive without disease progression are censored at date of last disease evaluation.
- Time to Progression: Time to Progression (TTP) is defined as the time from randomization (or registration) to progression, or censored at date of last disease evaluation for those without progression reported.

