1.2 Primary Objectives

1.2.1 To assess the clinical benefit (complete response + partial response or stable disease > 24 weeks) of the combination of PLD and pembrolizumab in patients with platinum resistant recurrent ovarian cancer. Initially, a six patient safety lead in will be performed of these 2 drugs combined together when used to treat patients with recurrent ovarian, peritoneal or fallopian tube cancer. If no more than 1 patient of the first 6 patients has evidence of dose limiting toxicities, an additional 20 patients will be added to complete the phase II study.

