13.1 Study Design/Endpoints

Primary safety endpoint:

- Dose limiting toxicity that occur during the first 4 weeks of treatment, as defined in Section 5.4

For the safety run-in using cohorts of 6 patients at any dose level, the following table gives the probability of continuing to the phase II portion of the study under varying true rates of dose-limiting toxicity.

	Acceptable dosage using 6 subjects						
True DLT rate	0.1	0.2	0.3	0.4	0.5	0.6	0.7
Probability	89%	66%	42%	23%	11%	4%	1%

Primary efficacy endpoint:

- Clinical benefit rate (CR + PR + SD \geq 24 weeks)

Secondary endpoints include:

- Toxicity by CTCAE version 4.0
- Objective response by RECIST 1.1.
- Progression-free survival
- Overall survival
- Time to progression
- Duration of response

Patients who withdraw study consent before receiving any study treatment will be replaced.

Patients who are receive study treatment, but who go off-treatment or off-study in cycle 1 and are not evaluable for DLT will be replaced for the safety run-in, but will be considered as non-responders in the final efficacy analysis.

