13.2 Sample Size, Accrual Rate and Study Duration

Because of the possibility that both objective response and prolongment of progression –free intervals are enhanced when chemotherapy and immune checkpoint blockade inhibitors are combined, the primary endpoint of this study is clinical benefit rate, using an interval of at least 24 weeks of stable disease. Pujade-Lauraine et al reported a 12% objective response rate in control arm to the AURELIA of single-agent chemotherapy for platinum-resistant ovarian cancer; the probability of being progression-free at 6 months was approximately 20%.

Therefore, a true clinical benefit rate of 25% or less would not be of clinical interest, and is the null hypothesis to a binomial test for a single-stage A'Hern design. A true clinical benefit rate of 50% would be considered a clinically meaningful level of response. Sample size was chosen to have high power ($\geq 90\%$) to declare the combination effective at this rate, while controlling the one-sided Type I error at no more than 10% under the null (exact alpha = 0.091)

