13.4 Analysis of Primary Endpoints

Under the exact binomial test, if clinical benefit is seen at least 10 of 26 patients (38%), the null hypothesis will be rejected and the regimen will be considered worthy of further study. The observed clinical benefit rate will be reported with a two-sided 90% exact confidence interval.

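### The stable-disease duration rule can count a patient as clinical benefit on the week-24 scan that first shows progression, depending on the day of the scan

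*Combined protocol and SAP*

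**What the plan says.** The primary efficacy endpoint in section 13.1 is the clinical benefit rate: CR, PR, or SD of 24 weeks or longer. Section 13.2 repeats this as "using an interval of at least 24 weeks of stable disease". The primary objective in section 1.2 has a strict inequality instead: "stable disease > 24 weeks".

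The only rule for how long SD has lasted is in section 11.1.4: "Stable disease is measured from the start of the treatment until the criteria for progression are met". Tumor assessments are every 8 weeks with a window of 1 week either side (sections 10 and 11.1). The plan does not say whether the window is counted from treatment start or from the previous scan.

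Section 13.2 sets the null with the statement that "a true clinical benefit rate of 25% or less would not be of clinical interest". Part of the rationale is a single-agent chemotherapy control arm in which "the probability of being progression-free at 6 months was approximately 20"%. Section 13.4 rejects the null if at least 10 of 26 patients have clinical benefit.

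**The concern.** The 24-week threshold coincides with the third scheduled scan, and the duration rule ends SD at the scan where progression is found, not at the last scan that showed SD. A patient whose third scan shows progression can therefore have an SD duration of 24 weeks or more and be counted as clinical benefit. Another patient with the same disease course, scanned a few days earlier inside the permitted window, is a failure.

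For these patients the literal rule can only add successes compared with requiring a progression-free week-24 scan. In an unrandomized study of 26 patients decided by one cut-off, one or two such patients could matter. They are also not progression-free at 6 months, which is the outcome cited as background for the null.

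**Working it through.** **1. The plan's own figures.** Inputs: n = 26, rejection at 10 or more, null 25%, alternative 50% (sections 13.2 and 13.4). The exact binomial tail gives P(X ≥ 10 | 26, 0.25) = 0.0909, which rounds to the stated 0.091, and P(X ≥ 10 | 26, 0.50) = 0.916, which meets the stated 90%. Both are right.

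**2. Date arithmetic.** 24 weeks = 24 × 7 = 168 days. If the window is anchored to treatment start, the third scan falls on 168 ± 7 = days 161 to 175, which is 15 permitted days. For a patient without prior CR or PR, stable at weeks 8 and 16, with first PD on the third scan, SD duration equals the scan day:

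| Scan day (elapsed) | Weeks | Under ≥24 (13.1, 13.2) | Under >24 (1.2) |
|---|---|---|---|
| 161–167 | 23.0–23.9 | failure | failure |
| 168 | 24.0 | benefit | failure |
| 169–175 | 24.1–25.0 | benefit | benefit |

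So 8 of 15 days give benefit under ≥ and 7 of 15 under >. If the first dose is called day 1, the cut moves by one day. If each interval may vary by a week, the third scan can fall anywhere from 3 × 49 = 147 to 3 × 63 = 189 days, and the dependence on scan timing widens.

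**3. Does another section close the gap?**
- Section 11.1.3.3 back-dates progression to the first scan, but only for an equivocal new lesion that is later confirmed.
- Section 11.1.3.4 asks that SD be documented at least 4 weeks from baseline, and a footnote limits even that to trials with response as primary endpoint. It sets nothing at 24 weeks.
- The 4-week repeat scan (sections 10 and 11.1.3.1) concerns staying on therapy and gives no progression date.
- The non-responder rule in section 13.1 covers only treated patients "who go off-treatment or off-study in cycle 1 and are not evaluable for DLT".
- The SD item in section 11.1.4 mentions neither death nor censoring, unlike the response-duration items beside it.

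**4. Size, on assumed curves.** The documents do not give the share of patients whose first progression is at the third scan. Assume progression-free curves with S(6 months) = 0.20, and 6 months = 26.09 weeks. Then S(t) = exp[−ln 5 × (t/26.09)^k]. The exponential has k = 1. A Weibull with median m months has k = ln(ln 5/ln 2)/ln(6/m). The 3- and 4-month medians read section 2.2's PFS of about 3–4 months for PLD as a median.

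| Curve | S(16) | S(24) | First PD at third scan | Of 26 |
|---|---|---|---|---|
| Exponential | 0.3727 | 0.2275 | 14.5% | 3.8 |
| Weibull, median 3 (k = 1.215) | 0.4113 | 0.2336 | 17.8% | 4.6 |
| Weibull, median 4 (k = 2.078) | 0.5583 | 0.2584 | 30.0% | 7.8 |

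Assume further that scan days are spread evenly over the 15 days and that 0% to 30% of these patients already count through CR or PR. The number counted as benefit despite PD on that scan is (of 26) × 8/15 or 7/15 × 0.7 to 1.0:
- Exponential: 1.4–2.0 (≥) or 1.2–1.8 (>).
- Weibull, median 3: 1.7–2.5 (≥) or 1.5–2.2 (>).

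The 4-month case is not carried further, because it joins a figure for recurrent disease in general to a 6-month figure from a platinum-resistant control arm.

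**5. What a visit-based rule would leave.** Patients who cross the progression threshold between weeks 23 and 25 would still depend on scan day. On the same curves, 26 × [S(23) − S(25)] is 26 × (0.2420 − 0.2139) = 0.7 for the exponential and 26 × (0.2898 − 0.2292) = 1.6 for the 4-month Weibull, against 3.8 and 7.8 exposed to scan day under the literal rule.

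**The case against.** The best defense is that nothing stated is wrong. The rule gives one answer for each date. Dating the end of SD to the scan where progression is found is the same convention the plan uses for PFS, time to progression and duration of response. On that convention, progression found on day 170 means 170/7 = 24.3 weeks without documented progression. A visit-based landmark is then a design preference. It does not abolish dependence on scan day, and it accepts SD seen on days 161 to 167 although the plan asks for at least 24 weeks. The size rests on assumed curves and an unstated anchor.

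Much of this stands. The rule is determinate, the size is an assumption, and the residual dependence is real and should be disclosed. But the convention suits time-to-event summaries. Here the duration is cut into success or failure at a threshold that coincides with a scan, so the scan that shows progression can earn the success. No section says this is intended, and the week-24 scan is already scheduled, so requiring it to be free of progression needs no new procedure.

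A reader might infer that the true type I error exceeds 10%. The documents do not support that. The stated alpha holds for a 25% null on the endpoint as counted, and that null is a judgment for a composite that also counts CR and PR of any duration. Nor can the third-scan share simply be added to the 20% benchmark: the share covers weeks 16 to 24, while the benchmark is at 6 months, and the same curves already give 22.8% to 25.8% progression-free at week 24.

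**Conclusion.** The point holds as a gap in the endpoint definition that should be closed before the primary analysis. Read literally, section 11.1.4 with sections 13.1 and 13.2 lets a non-responder with first progression on the third scan count as clinical benefit on days 168 to 175 (169 to 175 under the wording of section 1.2) and as a failure on days 161 to 167, given a window anchored to treatment start. For these patients the effect runs only towards more counted successes.

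The size is illustrative: roughly 1 to 2.5 of 26 patients under the exponential and 3-month Weibull curves, with evenly spread scan days. Larger figures need the weakly supported 4-month curve. The finding does not show that the 25% null, the 10-of-26 cut-off, the alpha or the power is wrong, nor that the decision would change.

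**What to change.** In sections 13.1 and 13.4, state that:
- the SD component requires a week-24 assessment, scheduled from treatment start with a window of ±1 week, that shows no RECIST 1.1 progression;
- progression or death first recorded at or before that assessment is not clinical benefit, whatever the day, while CR and PR are counted as now;
- if the week-24 scan is missing, the patient counts as benefit only if a later scan, done before any new anticancer therapy, shows no progression, and otherwise counts as a failure. This is a new rule, and the therapy condition is needed because section 5.5.3 prohibits no therapies in post-treatment follow-up;
- for the analysis, confirmed progression is dated to the first scan showing it, extending section 11.1.3.3. Rules for staying on therapy are not touched.

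State the scan anchor, align section 11.1.4, use one inequality in sections 1.2, 13.1 and 13.2, and say that the 25% null applies to this definition.

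The cost is a few sentences, with no new scans or patients and no change to 10 of 26, alpha or power. Three downsides should be disclosed. The observed rate may be slightly lower. SD seen on days 161 to 167 is accepted under the visit window, a small departure from 24 full weeks. Some dependence on scan day remains for progression between weeks 23 and 25, about 0.7 to 1.6 of 26 on the assumed curves, which is less than under the literal rule.
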